#### 1.3.3 Secondary Objectives

1. To determine whether the adjunct maze procedure improves the rate of return to stable SR at 24 months after surgery.

2. To determine whether the adjunct maze procedure decreases thromboembolic neurological complications (eg. stroke).

3. To determine whether the adjunct maze procedure enables anticoagulant treatment to be withdrawn safely.

4. To determine whether the adjunct maze procedure enables safe reduction or withdrawal of antiarrhythmic medication.

5. To determine whether the adjunct maze procedure is cost effective compared to the routine procedure.

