### 2.2 Secondary outcomes

Clinical endpoints of SR at 24 months after surgery, overall survival and stroke-free survival, incidence of anticoagulant-related haemorrhage.

Health-related QoL measured by the EuroQoL, SF-36 and NYHA.

Resource use and cost-effectiveness of the adjunct maze procedure.

Anticoagulant and antiarrhythmic drug usage.

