## 5.8 Additional Secondary Endpoint Analyses

To investigate whether the adjunct maze procedure decreases thromboembolic neurological complications (e.g. stroke), the patients who have suffered a stroke will be summarized within 12 months of surgery and the overall proportion of stroke events will be calculated by treatment group, using the total number of patients participating in the trial as the denominator. The absolute differences between the proportions for Routine treatment group and Routine+Maze group will be tested by Fisher's exact test, and reported along with 95% confidence intervals for differences in proportions.

The number of recruited patients who use anti-arrhythmic drugs will be tabulated by time points (at baseline, discharge, 6 weeks, 6 months, 12 months and 24 months) and drug categories (Sotalol, Amiodarone and Flecainade). Logistic Regression for the outcome of each patient (1=have one or more drugs during time period t, 0=have no drug during time period t) will be fitted, including drug category, time period using drug, baseline drug usage and treatment group as independent variables. The odds ratio for using anti-arrhythmic drug in the Routine treatment group relative to the Routine+Maze group will be reported with 95% confidence interval and p-value for the data seen, under the null hypothesis that the usage of anti-arrhythmic drugs is no different between the groups.

In the similar way, the number of recruited patients who use anti-coagulant drugs will be tabulated by time point (at baseline, discharge, 6 weeks, 6 months, 12 months and 24 months) and drug categories (Warfarin, Sintrome and other anticoagulants). The logistic regression for the outcome of each patient (1=have one or more drugs during time period t, 0=have no drug during time period t) will be fitted, including the drug category, time period using drug, baseline drug usage and treatment group. The odds ratio of using anti-coagulant drug in the Routine treatment group relative to the Routine+Maze group will be reported with 95% confidence interval and p-value for the data seen, under the null hypothesis that the usage of anticoagulants drug is no different between the pairs of groups.

The occurrence of atrial flutter and atrial tachycardia ("organised atrial arrhythmia" - OAA) and junctional rhythm (JR) will be summarised by arm. An exploratory analysis will look at the relation between the completeness of the lesion set and the occurrences of OAA and JR.

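### Objectives 3 and 4 ask about drug withdrawal, but section 5.8 reports only one odds ratio of any use per drug class, which mixes continuing among baseline users with starting among non-users

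*SAP*

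**What the plan says.** Section 1.3.3 of the SAP sets two objectives on medication. Objective 3 is "To determine whether the adjunct maze procedure enables anticoagulant treatment to be withdrawn safely". Objective 4 is "To determine whether the adjunct maze procedure enables safe reduction or withdrawal of antiarrhythmic medication".

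Section 2.2 names the matching outcome more loosely: "Anticoagulant and antiarrhythmic drug usage".

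Section 5.8 codes the outcome for each patient as "1=have one or more drugs during time period t, 0=have no drug during time period t" and fits a logistic regression "including drug category, time period using drug, baseline drug usage and treatment group as independent variables". The result for the first class is stated thus: "The odds ratio for using anti-arrhythmic drug in the Routine treatment group relative to the Routine+Maze group will be reported". The test is made "under the null hypothesis that the usage of anti-arrhythmic drugs is no different between the groups". Anticoagulants are handled the same way: "The odds ratio of using anti-coagulant drug in the Routine treatment group relative to the Routine+Maze group will be reported".

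Neither model is restricted to patients taking the drug at baseline. Section 1.6 does not make drug use an entry criterion, section 3.1 makes all randomised patients the primary population, and a baseline-use covariate would be constant if only users were analysed. Section 5.8 has no treatment-by-baseline-use term, although section 5.5 specifies interactions of that kind for other variables. It also tabulates numbers on each drug by time point.

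**The concern.** A patient on a drug at baseline can continue or stop. A patient not on it at baseline can start or not start, and may later stop what was started. Entering baseline use as a main effect gives the two groups different underlying levels of use but still imposes one treatment odds ratio on both. If the maze procedure affects the two groups differently, the reported figure is a weighted average of the two effects. The weights depend on how many patients were on the drug at the outset.

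Two errors of interpretation then become possible. A lower odds of use in the maze arm could be read as withdrawal when it came wholly from fewer new prescriptions. Conversely, a real difference in stopping could be cancelled by new starts in the other direction. The tables by time point do not settle this, because they give net numbers on the drug, not who stopped. No planned analysis isolates stopping, so objectives 3 and 4 would have no estimate of their own.

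**Working it through.** **Inputs from the SAP.** 200 per arm (section 1.4.1); two-sided 5% level (section 5.1); logistic model with baseline use and treatment as main effects (section 5.8). The SAP states no figure for drug use, so there is none to reproduce.

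**Assumed inputs.** The share on the drug at baseline, the share of those still on it, and the share of non-users newly on it. All are varied below. The model has a single visit and omits the drug-category and time-period terms, so the results illustrate the mechanism and do not predict the trial's result.

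**Method.** Fit logit P(use) = a + b × baseline use + t × arm to the expected counts. The pooled odds ratio (OR), routine relative to maze, is exp(t). The chance of significance is Φ(|t|/SE − 1.96) plus the negligible opposite tail.

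**1. Identical stopping, different starting.** Half of baseline users are still on the drug in each arm, so the OR among users is (0.5/0.5)/(0.5/0.5) = 1.00.

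| Baseline users | Pooled OR, starts 25% v 10% | Chance significant | Pooled OR, starts 15% v 10% | Chance significant |
|---|---|---|---|---|
| 20% | 2.10 | 83% | 1.34 | 19% |
| 30% | 1.83 | 70% | 1.26 | 15% |
| 40% | 1.63 | 55% | 1.20 | 11% |
| 70% | 1.23 | 16% | 1.07 | 6% |
| 90% | 1.06 | 6% | 1.02 | 5% |

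The 40% row shows the mechanism for starts of 25% v 10%. Routine has 80 × 0.5 + 120 × 0.25 = 70 patients on the drug; maze has 80 × 0.5 + 120 × 0.10 = 52. The difference of 18 is made up entirely of new starts.

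**2. Different stopping, opposite starting.** Take 50% baseline users, 70% v 55% of them still on the drug, and starts of 10% v 25%. Routine has 100 × 0.70 + 100 × 0.10 = 80 on the drug; maze has 100 × 0.55 + 100 × 0.25 = 80. The pooled OR is 1.00 (95% CI 0.64 to 1.57). The OR among users is (0.70/0.30)/(0.55/0.45) = 1.91, and among non-users (0.10/0.90)/(0.25/0.75) = 0.33.

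**3. Different stopping, equal starting.** With 60% v 40% of users still on the drug, the OR among users is (0.6/0.4)/(0.4/0.6) = 2.25. With starts of 15% in both arms and 20/30/40% baseline users, the pooled OR is 1.30/1.44/1.58 with power 18/32/48%. Baseline users alone give 43/59/71%.

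**4. The same effect in both groups.** Users 60% v 40% and starts 20% v 10% both give OR 2.25, since (0.2/0.8)/(0.1/0.9) = 2.25. The pooled model then returns 2.25 with power 86% to 91% at 20-40% baseline users, against 43% to 71% in baseline users alone.

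**The case against.** The planned odds ratio does what section 2.2 and the stated null hypotheses call for: it compares usage between randomised arms, adjusted for baseline. Omitting an interaction is ordinary practice, and the population follows section 3.1. If the effect is common to both groups, pooling is clearly the more powerful choice (step 4). These are additional secondary analyses, with no bearing on the primary endpoints or on sinus rhythm at 24 months. All of this stands, and it is why the pooled odds ratio should be kept.

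A reader might go further than the SAP supports in three ways.

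- *Only baseline users can withdraw.* Use is recorded at discharge, 6 weeks, 6, 12 and 24 months. A patient who starts a drug around surgery can be off it later, and objectives 3 and 4 do not exclude such patients. An analysis of baseline users alone would miss them.
- *The plan will report a false withdrawal effect.* Section 5.8 speaks of use, not withdrawal, and the large distortions need strongly different starting rates and few baseline users.
- *The problem is worse for anti-arrhythmics.* That would need baseline use by class, which the SAP does not give.

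What the objection does not meet is the gap itself: the objectives ask about withdrawal, and no planned analysis estimates it.

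**Conclusion.** The point holds as a mismatch between objective and estimate. The section 5.8 odds ratio is sound for usage but cannot by itself answer objectives 3 and 4, because different combinations of stopping and starting can produce the same value. Under the assumed one-visit model, the pooled figure ranges from 2.10 with no difference in stopping to 1.00 with a real one. The distortion is modest when starting rates differ little, and nearly absent when about 90% of patients are on the drug at baseline. These sizes rest on assumed rates, and the true size is unknown for either class. This is an inexpensive improvement to a secondary analysis and does not touch the trial's main conclusions.

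**What to change.** Amend section 5.8 for both drug classes:

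- Keep the pooled odds ratio, labelled as a comparison of overall usage.
- Add a treatment-by-baseline-use term and report the treatment effect, with 95% confidence interval, separately in baseline users (still on the drug v off it) and in baseline non-users (on the drug v not), by randomised arm, at 12 and 24 months. Report both whether or not the interaction is significant.
- Base any statement about withdrawal of pre-operative treatment on the baseline-user estimate.
- Describe separately, by arm, the stopping of drugs first started at or after surgery. Whether a drug was started is itself determined after randomisation, so this should stay descriptive.

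Section 4.2 places baseline measurements before randomisation, so splitting by baseline use preserves the randomised comparison. No new data are needed, only SAP wording, one model term and one table. The price is precision: the withdrawal estimate rests on fewer patients and has a wider interval than the pooled odds ratio. For example, with 30% baseline users (60 per arm) and half still on the drug in each arm, SE(log OR) = √(4/30) = 0.365, so an odds ratio of 1.00 has a 95% interval of 0.49 to 2.05. If the effect really is the same in both groups, the pooled model remains the more powerful.

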### 5.1 General calculations

All statistical analyses and reporting will comply with CONSORT guidelines where possible.

Confidence intervals for a single proportion shall be calculated using the Exact method. Confidence intervals for a difference between independent proportions shall be calculated using Exact intervals (Method 8 of [16]).

All percentages will be calculated using the total number of patients within the specified analysis population, percentages will be reported to 1 decimal place. All statistical tests will be 2-sided and performed at the 5% significance level. All analyses will be carried out using SAS.

For summary statistics, the number of non-missing items, the means, standard deviations, medians, upper and lower quartiles and minima and maxima will be summarised to one more decimal place than the data are collected.

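### Objectives 3 and 4 ask whether drugs can be withdrawn safely, but SAP 5.8 compares only any-versus-no drug use by arm, and the percentage rule in 5.1 lets deaths and losses lower apparent use

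*SAP*

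**What the plan says.** SAP 1.3.3 sets two secondary objectives on drugs. Objective 3 is "To determine whether the adjunct maze procedure enables anticoagulant treatment to be withdrawn safely". Objective 4 is "To determine whether the adjunct maze procedure enables safe reduction or withdrawal of antiarrhythmic medication". SAP 2.2 lists "incidence of anticoagulant-related haemorrhage" among the secondary outcomes.

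The drug analyses are in SAP 5.8. First, "the number of recruited patients who use anti-coagulant drugs will be tabulated by time point", from baseline to 24 months, and antiarrhythmics are handled likewise. Then a logistic model is fitted to an outcome coded "1=have one or more drugs during time period t, 0=have no drug during time period t", with drug category, time period, baseline use and treatment group as covariates. The anticoagulant odds ratio is reported "under the null hypothesis that the usage of anticoagulants drug is no different between the pairs of groups"; the antiarrhythmic null is equivalent. The antiarrhythmic table uses "drug categories (Sotalol, Amiodarone and Flecainade" and stops there, whereas the anticoagulant list ends with a category for other agents.

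The same section summarises stroke within 12 months of surgery and compares the arms by Fisher's exact test with a confidence interval. SAP 5.9 summarises adverse events and deaths by the intervention received.

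On denominators, SAP 5.1 states: "All percentages will be calculated using the total number of patients within the specified analysis population". SAP 3.1 defines the intention-to-treat population as everyone randomised, including those who withdrew or were lost, apart from patients whose consent is withdrawn or missing.

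**The concern.** The objectives carry a safety condition that the drug models do not. A patient who comes off anticoagulant and then has a stroke or a bleed is coded 0, exactly like one who comes off it and stays well. The odds ratio can favour the maze arm in either case. Any-versus-none coding also cannot show a reduction short of stopping, which objective 4 names.

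The other safety analyses do not close the gap. The stroke summary ends a year before the last drug-use visit. Haemorrhage is a declared outcome without its own analysis in section 5. Sinus rhythm at 24 months (SAP 5.6) is analysed separately from antiarrhythmic use.

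The denominator rule adds a second, smaller problem. A patient who is dead or lost stays in the denominator of a drug-use percentage but cannot be in its numerator, so the percentage of users falls at later visits without anyone having stopped a drug.

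**Working it through.** **Step 1: objective against analysis.** The SAP gives no figure to reproduce here, so the sections are set side by side.

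| Needed for safe withdrawal | Where the SAP treats it | Gap |
|---|---|---|
| Off the drug | 5.8: any versus none, to 24 months | No event or rhythm in outcome or covariates |
| Free of stroke | 5.8: by arm, within 12 months | Months 12 to 24 not covered; no link to drug status |
| Free of anticoagulant-related haemorrhage | Listed in 2.2 | No comparison by randomised arm in section 5 |
| Alive | 5.9: by intervention received | Not by randomised arm; no link to drug status |
| In SR (bears on antiarrhythmics) | 5.6: by arm at 24 months | Not combined with drug use |

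An assumed example shows the effect. Let 50% of the maze arm and 30% of the routine arm be off the drug. Use is then 50% and 70%, and the unadjusted odds ratio for use, routine relative to maze, is (0.70/0.30) / (0.50/0.50) = 2.33. It stays 2.33 whatever happens to the patients who stopped, because events are not in the outcome.

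**Step 2: the denominator.** Let u be the proportion using the drug among patients still assessed, and L the proportion dead or lost. Under SAP 5.1 and 3.1 the percentage shown is u × (1 − L). The SAP gives no rate of drug use, so 40%, 60% and 80% are assumed. For L, SAP 1.4.1 speaks of about 15% at 12 months, while its own numbers give 1 − 352/400 = 12%; 5% is added as a low value.

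| Assumed use | L = 5% | L = 12% | L = 15% |
|---|---|---|---|
| 40% | 38.0% | 35.2% | 34.0% |
| 60% | 57.0% | 52.8% | 51.0% |
| 80% | 76.0% | 70.4% | 68.0% |

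At 60% use, for example, 0.60 × 0.85 = 0.51, so apparent non-use is 49% rather than 40%.

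**Step 3: the comparison between arms.** If use and L are the same in both arms, the difference shown is zero: 52.8% against 52.8% at 60% use and 12% loss. A false difference needs unequal losses. The table assumes equal true use and the losses shown (routine / maze). The odds ratio applies only if dead and lost patients were coded 0, which the SAP does not state.

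| Assumed use | Losses 10% / 14%: gap in points, odds ratio | Losses 5% / 15%: gap in points, odds ratio |
|---|---|---|
| 40% | 1.6, 1.07 | 4.0, 1.19 |
| 60% | 2.4, 1.10 | 6.0, 1.27 |
| 80% | 3.2, 1.17 | 8.0, 1.49 |

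Check at 60% use with 5% / 15%: 57% against 51%, and (0.57/0.43) / (0.51/0.49) = 1.27.

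**The case against.** The strongest reply is that safety is examined. Stroke is compared by arm with a test and an interval, deaths and adverse events are summarised by treatment group, and SAP 5.9 refers to pre-specified adverse event categories that it does not list and that might include haemorrhage. Reading drug use beside these results is a legitimate way to weigh benefit against harm, and 5.8 never says that the drug-use test alone settles objective 3. This stands in part: it would be wrong to say that the plan ignores safety, or that only a joint outcome could address it. It does not fill the gaps on stroke after 12 months, on haemorrhage by randomised arm, or on how the pieces together are to answer the word safely.

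A second reply is that a joint outcome can mislead too. Take the example in step 1 and assume stroke in 6% of the maze arm and 2% of the routine arm, independent of drug status. Joint success is 0.50 × 0.94 = 47% against 0.30 × 0.98 = 29%, so the maze arm looks better with three times the strokes. This is correct, and it is why each component must be reported beside the joint result. Selecting patients by drug use at discharge would also condition on something that happens after randomisation; baseline use precedes it (SAP 4.2).

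Three stronger readings are tempting but not supported:

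- A reader might infer that dead and lost patients are coded as non-users in the model. SAP 5.8 promises counts and an odds ratio, and nothing assigns those patients a 0. Only the percentage denominator is fixed by rule.
- A reader might infer that a patient switched to an unlisted antiarrhythmic counts as withdrawn. The three drugs are named as table categories, and the SAP does not say that others are coded 0.
- A reader might infer that surgeons who know the allocation drive later drug use. SAP 1.2 does not list them as blinded, but the SAP does not say who decides on these drugs after surgery.

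**Conclusion.** The point holds. Followed exactly, the SAP can show whether drug use differs between arms but not whether withdrawal was safe, so it does not answer objectives 3 and 4 as worded. This rests on the text alone and needs no assumed rates.

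The denominator effect is certain for any drug-use percentage reported under SAP 5.1. At 12% to 15% dead or lost it lowers an assumed 60% use by 7.2 to 9 points, and across 40% to 80% use by 4.8 to 12 points. It does not bias the arm comparison when use and losses are equal. An effect on the odds ratio is possible but not stated. The use rates and the unequal losses are assumptions, not figures from the SAP.

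Both problems concern secondary objectives and leave the two primary analyses untouched. The change should be made, since it is cheap.

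**What to change.** In SAP 5.8:

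1. Report drug-use percentages at each visit over patients alive with drug data, showing dead and not-assessed patients separately. State that they are not coded 0 in the logistic models.
2. Add a 24-month outcome by randomised arm, among patients using the drug class at baseline only. For anticoagulants: alive, off the class, and free of stroke/thromboembolism and anticoagulant-related haemorrhage. For antiarrhythmics: alive and off the class, reported with the 24-month rhythm. Always show each component separately, so that fewer users cannot mask more events. State how patients not assessed at 24 months are handled.
3. Compare stroke/thromboembolism and anticoagulant-related haemorrhage by randomised arm to 24 months.
4. Add a category for other antiarrhythmics, to match the anticoagulant list.

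Keep the existing drug-use comparison, but do not present it alone as evidence of safe withdrawal. The outcome in item 2 captures stopping only, so 5.8 should also say whether the reduction named in objective 4 will be assessed.

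The cost is SAP wording and a few derived variables. SAP 4.3 already lists medications, mortality, stroke/thromboembolic events, 4-day ECGs and adverse events as collected. The downside is that joint success rates will be lower than plain withdrawal rates. These changes define analyses only and set no rule for stopping a drug.

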## 5.9 Safety Analysis

A listing of total number of adverse events in each category as well as the deaths from any cause will be presented, and summarised by treatment group, corresponding to the intervention received. Events will be summarised according to whether they meet the

criteria of Serious Adverse Events, and whether they are thought to be related to the procedure.

Adverse Events are not planned to be categorised. However, a number of pre-specified Adverse Event categories have been specified.

Health Economic Analysis will be performed by the Health Economic Analysis team. A separate analysis plan has been written, and should be referred to for a description of the planned analyses.

